2.2. Efficacy Measures Summary: All Analyses Adjusted Similarly to the Primary Analysis

- **Primary Efficacy Analysis:** Dichotomized, adjudicated, cross-sectional mRS 0-3 vs. 4-6 at 365 days post-ictus, adjusting for baseline (pre-randomization) variables used in covariate adaptive randomization as well as the clinically established severity variables IVH size and ICH location (lobar or deep).
- Additional, Exploratory Analyses of mRS at 365 days:
 - a. Dichotomized, adjudicated, cross-sectional mRS 0-3 vs. 4-6 at 365 days post ictus, adjusting for baseline (pre-randomization) variables used in covariate adaptive randomization as well as additional baseline variables determined to be associated with the outcome.
 - b. Ordinal, adjudicated mRS (0-6) at 365 days.
 - c. mRS 0-3 vs. 4-6 at 365 days based on a full longitudinal analysis of the mRS data at 90, 180, and 270 days.
 - d. Severity subgroup analyses (including, but not limited to, IVH size, location of ICH, presentation co-morbidities such as diabetes, CVD, and white matter disease, etc.)
 - e. Cross-sectional of mRS 0-3 vs. 4-6 for demographic subgroups of patients, including for race and gender. (For d and e, see section 5.5.)
 - f. Analysis of cross-sectional mRS 0-3 vs. 4-6 at 365 days that models random effects for hospital sites.

• Secondary Analyses of other outcomes

- 1. Dichotomized eGOS UGR-US vs. LS-Death at 365 days.
 - Subordinate: Ordinal eGOS UGR, LGR, MD, LM, US vs. LS, VS, Death at 365 days.
- 2. All-cause mortality longitudinally from ictus to 365 days.
 - Subordinate: Predictors of mortality.
- 3. Relationship between clot removal as an AUC clot-assessment that estimates the timeweighted clot volume from ictus to end of treatment (EOT; i.e., 24 hours after last dose) as AUC clot exposure and functional outcome (proportion 0-3 mRS).
- 4. Patient disposition:
 - a. Home days over 365 days' time from ictus.
 - b. Patient location at 365 days post ictus (i.e., good vs. bad location. See Tertiary 2g for definition.)
- 5. 180-day efficacy:
 - a. Dichotomized, adjudicated, cross-sectional mRS 0-3 vs. 4-6.
 - Subordinate (1): Ordinal, adjudicated mRS (0-6).
 - b. Dichotomized, adjudicated eGOS UGR, LGR, MD, LM, US vs. LS, VS, Death.
 - Subordinate (2): Ordinal, eGOS UGR, LGR, MD, LM, US vs. LS, VS, Death.
 - Subordinate analyses 2-5 as defined under the Primary but for eGOS.
- 6. Type and intensity of ICU management:
 - a. ICU days

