8.0. Multiplicity

The primary analysis of efficacy is tested at the two-sided alpha level of 0.05. In addition, secondary analyses will consider the alpha=0.05 two-sided type I error. Secondary analyses will be examined in the order specified and will not be corrected for multiplicity of testing.

Secondaries 2-7 are defined. The other analyses without specific hypotheses are considered exploratory. We will present descriptive statistics and CIs.

For safety outcomes, we do not account for multiplicity as this study was not powered to observe safety. Thus, a cautionary approach is justified.

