11.0. Efficacy Analyses

11.1. Primary Efficacy Analysis: Dichotomized, Adjudicated mRS 0-3 vs. 4-6 at 365 Days Post Ictus

This primary analysis will produce an estimate and 95% confidence interval for the average treatment effect comparing assignment to MIS+rt-PA treatment (MISTIE) versus control (standard of care, i.e., medical management), using the ITT principle. Specifically, we will estimate the difference between the probability of an adjudicated mRS score of 3 or less at 365 days post-stroke comparing assignment to

treatment versus control; this difference is called the average treatment effect. Below is a description of the procedure for computing estimators of the average treatment effect. We also will test the null hypothesis of zero treatment effect at level 0.05.

To estimate the average treatment effect, we will use the targeted maximum likelihood estimator (TMLE) of van der Laan and Gruber.³ This estimator adjusts for baseline (i.e., pre-randomization) variables in order to improve precision. The baseline variables, denoted by the vector B, include the three variables used in the covariate-adaptive randomization as given in Section 6.0 (i.e., pre-randomization clot volume, age, and baseline severity of impairment as measured by GCS) as well as the following additional variables: IVH volume and location of ICH (indicator of lobar vs. deep). All baseline variables are treated as categorical and included as main terms in the models below.

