The 95% confidence interval will be computed by the non-parametric bootstrap (resampling participants with replacement and recomputing the above estimator), and using the bias corrected and accelerated (BCa) method.⁵ The null hypothesis of zero average treatment effect will be rejected if this confidence interval excludes 0. This completes the description of the primary efficacy analysis, except for how missing baseline variables and intermittent (non-monotone) missingness are handled, as described next.

Missing baseline variables are imputed using the median for continuous-valued variables and mode for categorical variables. This and the following paragraph are done before any of the steps above.

We next describe how intermittent (non-monotone) missing data are handled, such as when a participant misses the 30-day visit only. We consider each interim visit at v=30 and 180, in turn. First, for visit v=30 days, we fit a multinomial logistic regression for M_{30} given A, B among those with C_{30} =1; for those with C_{30} =0, we then set their M_{30} to be the value with highest predicted probability from the model fit. Next, for visit v=180 days, we fit a multinomial logistic regression for M_{180} given A, B, C_{30} , among those with C_{180} =1; for those with C_{180} =0, we set their M_{180} to be the value with highest predicted probability from the model fit. Next, for visit v=180 days, we fit a multinomial logistic regression for M_{180} given A, B, C_{30} , among those with C_{180} =1; for those with C_{180} =0, we set their M_{180} to be the value with highest predicted probability from the model fit. We do not apply this process to the final outcome at 365 days. All models include intercepts and main terms for the variables listed. Next, we modify model (1) to include the additional main term $C_{30}C_{180}$ and its interaction with A. Similarly, in model (2) we include the additional main term C_{30} and its interaction with A. The idea is that each model (1)-(2) now contains an indicator of whether the mRS score on the right side was directly measured or was predicted by the above process based on previous mRS measurements, study arm, and baseline variables.

Minimally Invasive Surgery Plus rt-PA for ICH Evacuation Phase 3

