12.0. Interim Efficacy Analyses

At the discretion of the DSMB, a formal interim efficacy analysis will occur after 375 subjects reach 180 days of follow-up. These analyses will be based on approximate O'Brien-Fleming stopping boundaries for efficacy (defined below).

In the MISTIE III design, subjects will be randomized to MIS+rt-PA versus medical management using a covariate-adaptive design described previously. The trial will initially enroll ICH patients until either a maximum of 500 eligible patients is accrued or the trial is stopped early for efficacy or futility using group sequential boundaries described below.

Analyses will be conducted after 375 and 500 patients, respectively, have 180-day post-stroke measurements. Efficacy stopping boundaries will be based on the error-spending (also called alpha-spending) approach using the power family with exponent rho=3, which approximates the O'Brien-Fleming boundaries. The (one-sided) alpha allocated to the analysis (called the interim analysis) at 375 participants is defined to be alpha₁ = $0.025(375/500)^3 = 0.0105$. All remaining alpha, i.e., (0.025-alpha₁) is spent at the analysis with 500 participants (called the final analysis).

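### The SAP 11.1 decision rule does not carry forward the alpha that SAP 12.0 spends at the discretionary efficacy look, and 12.0 leaves the interim endpoint and the meaning of crossing undefined

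*SAP*

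**What the plan says.** The SAP's primary endpoint is clear. Section 2.2 gives it as "Dichotomized, adjudicated, cross-sectional mRS 0-3 vs. 4-6 at 365 days post-ictus", and section 4.0 records the move from 180 to 365 days as deliberate.

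Section 8.0 sets the error rate: "The primary analysis of efficacy is tested at the two-sided alpha level of 0.05". Section 11.1 repeats it, "We also will test the null hypothesis of zero treatment effect at level 0.05", and then gives the operative rule for the 95% BCa bootstrap interval: "The null hypothesis of zero average treatment effect will be rejected if this confidence interval excludes 0". Section 11.1 adds that the primary analysis is then fully described except for missing baseline values and intermittent missing visits. It names no interim adjustment as outstanding.

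Section 12.0 sets out a group sequential scheme. The look is optional: "At the discretion of the DSMB, a formal interim efficacy analysis will occur after 375 subjects reach 180 days of follow-up". Both analyses are timed on 180-day data: "Analyses will be conducted after 375 and 500 patients, respectively, have 180-day post-stroke measurements". The interim spends one-sided 0.025(375/500)^3 = 0.0105, and the remainder "is spent at the analysis with 500 participants (called the final analysis". Enrolment continues to 500 "or the trial is stopped early for efficacy or futility using group sequential boundaries described below". Section 2.3.2 also times the look by the availability of 180-day outcomes.

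The protocol made the link that the SAP lacks. Protocol 9.1.7.a (Analysis 1a) bases rejection on the group sequential thresholds in Table 1, with a final value of 2.03, but for a 180-day endpoint.

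**The concern.** If the DSMB holds the look, an analyst who follows 11.1 compares the final statistic with 1.96 and one who follows 12.0 uses a larger value. A result between the two is positive under one section and negative under the other, and the choice would fall to be made with the data in hand. If crossing at the interim also counts as success, applying 11.1 unchanged takes the overall error above the level in 8.0.

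The gaps in 12.0 matter as much. The size of the excess, and the critical value that removes it, depend on whether the interim tests 180-day or 365-day mRS and on whether crossing rejects the 365-day null or only stops enrolment. The SAP says neither.

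**Working it through.** **Inputs.** Total one-sided alpha 0.025, power-family spending with rho = 3, looks at 375 and 500 (SAP 12.0). Final rule: 95% interval, taken as |z| > 1.96 (SAP 11.1). Accrual about 30 per arm per six months (SAP 14.4). Planning rates at 180 days, 250 per arm: 25% vs 38% and 20% vs 31% (Protocol 9.1.9). The calculation uses a normal approximation, does not model bootstrap error and includes no futility bound.

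**1. The plan's own figure.** 0.025 × 0.75³ = 0.010547, which matches 0.0105. The remainder is 0.025 − 0.010547 = 0.014453. The interim critical value is z₁ = 2.306.

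**2. Final critical value, same endpoint.** With corr(Z₁, Z₂) = √0.75 = 0.866, solve P(Z₁ ≤ 2.306, Z₂ > c) = 0.014453. This gives c = 2.022, a nominal one-sided level of 0.0216, two-sided 0.0432, or about a 95.7% interval.

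**3. Error if 1.96 is kept and crossing counts as success.** P(Z₁ > 2.306 or Z₂ > 1.96) = 0.0280 one-sided. The two-sided figure is 0.0530 with an interim bound on the benefit side only and 0.0560 with a symmetric one.

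**4. Error if crossing only stops enrolment.** P(Z₃₇₅ > 2.306, Zₙ > 1.96) + P(Z₃₇₅ ≤ 2.306, Z₅₀₀ > 1.96). If enrolment continues while the 375th patient completes 180 days, n is about 375 + 60 = 435, and the error is 0.0265. It ranges from 0.0280 (n = 375) to 0.0250 (n = 500).

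**5. Error if the look tests 180-day mRS and crossing counts as success.** The correlation becomes r × 0.866, where r is the correlation between the 180-day and 365-day statistics. The documents do not give r. Using 1.96, by assumption on r:

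| r (assumed) | One-sided error |
|---|---|
| 1 | 0.0280 |
| 0.8 | 0.0310 |
| 0 | 0.0353 |

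A final value of z = 2.185 (one-sided 0.01445) keeps the error at or below 0.0248 for any r from 0 to 1. If a 180-day crossing only stops enrolment, 1.96 gives 0.0257 at r = 0.8 and n = 435.

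**6. Sensitivity of the final value to the information fraction.**

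| Information | Interim alpha held at 0.0105 | Spending function re-evaluated |
|---|---|---|
| 70% | 2.04 | 2.01 |
| 75% | 2.02 | 2.02 |
| 80% | 2.01 | 2.03 |

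**7. Protocol rule for comparison.** With one look at 375 and bounds 2.34/2.03, the one-sided error is 0.0242; with Table 1's three looks it is 0.0247. The protocol's rule holds its level.

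**8. Power (unpooled standard error).**

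| Rates | Fixed, 1.96 | Two looks, 2.306/2.022 | Final test alone, 2.185 |
|---|---|---|---|
| 25% vs 38% | 88.5% | 87.9% | 83.5% |
| 20% vs 31% | 81.2% | 80.3% | 74.5% |

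**The case against.** Three points on the other side have force.

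First, 8.0 and the level stated in 11.1 can be read as the overall two-sided 0.05, which is exactly what 12.0 spends in total (2 × 0.025). On that reading those sentences agree with 12.0. This stands, and it confines the firm conflict to the interval rule in 11.1. It does not remove it, because that rule fixes the interval at 95% and 11.1 calls the description complete apart from missing data.

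Second, the look is discretionary. If it is not held, no alpha is spent and 11.1 is correct. This also stands; the conflict is conditional.

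Third, the effect is small: 2.8% against 2.5% needs the look held, crossing counted as success, one endpoint and 11.1 applied unadjusted. That is fair, and the figures above 2.8% rest on an assumed correlation. The r = 0 end is only a bound, since 11.1 itself models mRS at one visit from the previous one.

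Two stronger readings are tempting. A reader might infer that 12.0 leaves the final test only one-sided 0.0145, so that the gap is 0.05 against 0.029 two-sided. Section 12.0 does not say that: 0.0145 is error spent at the final analysis in addition to the interim. With correlated statistics the nominal level is 0.0216 one-sided, and testing at 0.0145 would bring the overall error down to 0.0190. A reader might also infer that the SAP has no alpha adjustment. It does, in 12.0; what is missing is the link to 11.1.

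**Conclusion.** The point holds in a limited form and should be fixed. If the look is held, SAP 11.1 and 12.0 give different final critical values, 1.96 and 2.02 at 75% information (two-sided 0.05 against about 0.043), and nothing says which governs. Overall one-sided error under 11.1 is then about 2.8% if crossing counts as success on the same endpoint, and about 2.65% if crossing only stops enrolment with 435 enrolled. It is larger if a 180-day crossing itself counts as success, for example 3.1% at an assumed correlation of 0.8. It is nominal if the look is not held.

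The missing link and the gaps in 12.0 are certain from the text. The error figures are less firm: they assume information proportional to patient count and approximate normality.

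**What to change.** **SAP 11.1, with a cross-reference in 8.0.** State that if the efficacy look is held, the final 365-day test uses the critical value from the 12.0 spending function (|z| > 2.02, about a 95.7% BCa interval, at 75% information), and that the 95% rule applies if it is not held. Keep the 95% interval for reporting.

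**SAP 12.0.**
- Use the 365-day primary endpoint at both analyses, or name the interim endpoint and test statistic.
- Say whether crossing rejects the 365-day null or only stops enrolment.
- Tie the final analysis to the 365-day primary.
- State whether the interim alpha stays at 0.0105 or is re-evaluated at the actual information fraction, since the final value moves in opposite directions under the two rules.

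A final value stricter than the same-endpoint one is needed only if a 180-day crossing itself rejects the 365-day null. In that case 2.185 is the upper bound that needs no correlation.

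**Cost.** A few sentences. The same-endpoint rule costs under 1 point of power at the 180-day planning rates (no 365-day control rate is given). The 2.185 bound would cost about 5 to 7 points on the final test, which is a reason to settle the meaning of crossing first. Aligning the protocol's 180-day primary with the SAP is a separate amendment.

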2.0. Objectives of the Study

2.1. Efficacy

The primary aim of this multicenter, international, randomized, open-label, phase 3 trial is to determine the efficacy of intra-clot catheter placement and aspiration of hematoma contents, followed by gentle clot irrigation with low dose recombinant tissue plasminogen activator (rt-PA), referred to as Minimally Invasive Surgery plus rt-PA (MIS+rt-PA). The primary hypothesis of this trial is that the MIS+rt-PA approach to intracerebral hemorrhage (ICH) management will result in more patients having overall better functional outcome at 365 days, as defined by the proportion of subjects with dichotomized, adjudicated modified Rankin Scale (mRS) score 0-3 vs. 4-6, when compared to the mRS scores for patients managed with standard aggressive medical treatment. Although the mRS includes a category for death, and hence the primary analysis incorporates mortality outcomes, in-hospital and 30-day mortality will also be examined as safety outcomes for the trial. Furthermore, 365-day mortality will be evaluated separately as a secondary efficacy outcome. An intent-to-treat (ITT) paradigm for the analyses will be incorporated. The MISTIE III trial will enroll a total of 500 eligible patients, 250 randomized each treatment arm (MIS+rt-PA or medical management). The power to detect (88%) is for an estimated effect size of 13% across all clot locations with this sample size (500).

Additional analyses of efficacy outcomes will evaluate the therapeutic benefit of MIS+rt-PA relevant to medical management in improving subjects' function and quality of life at 365 days post symptom onset as measured by extended Glasgow Outcome Scale (eGOS), days in various locations such as home

Minimally Invasive Surgery Plus rt-PA for ICH Evacuation Phase 3

during the 365-day period, patient disposition at 180 and 365 days including proportion of days in longterm care facilities, National Institutes of Health Stroke Scale (NIHSS), Barthel score, days in hospital, days in intensive care unit (ICU), Stroke Impact Scale (SIS), Preference-Based Stroke Index (PBSI), EuroQol-5 Dimension (EQ-5D), Mini-Mental State Examination (MMSE), Personal Health Utility Interview, and Center for Epidemiological Studies – Depression (CES-D).

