The TMLE estimator also involves adjustment with the goal of reducing bias due to informative censoring, that is, participant dropout that may be correlated with the primary outcome. The TMLE adjusts for missing outcomes through a combination of inverse probability of censoring weights and outcome prediction models. Specifically, the weights and prediction models use the aforementioned baseline variables, study arm, and the following post-randomization variables: mRS scores measured at 30, 180, 365 days from ictus, denoted M₃₀, M₁₈₀, M₃₆₅ respectively. The motivation is that if mRS score at a given visit is correlated with the mRS score at the next visit and also with dropout, then adjusting for observed differences in the mRS history of those who drop out versus those who stay on study may reduce bias (under the assumption that censoring is missing at random). As we describe below, this adjustment is implemented by fitting models for dropout and models for the primary outcome based on mRS measured at the previous visit, study arm, and baseline variables.

Let A denote the study arm, where A=1 for the MISTIE treatment arm and A=0 for the standard of care (medical management) arm. Let C_{30} , C_{180} , C_{365} denote the indicator of being uncensored at the 30-, 180-, 365-day visits, respectively. E.g., C_{180} =1 means the participant attended the 180-day visit and had his or her mRS M_{180} recorded.

The TMLE involves first constructing inverse probability of censoring weights W₃₀, W₁₈₀, W₃₆₅, defined as follows:

$$\begin{split} & W_{30} = 1/[\Pr(C_{30} = 1 \mid B, A) \; P(A \mid B)] \\ & W_{180} = W_{30}/\Pr(C_{180} = 1 \mid C_{30} = 1, B, A, M_{30}) \\ & W_{365} = W_{180}/\Pr(C_{365} = 1 \mid C_{180} = 1, B, A, M_{180}) \end{split}$$

where the probabilities are estimated by fitting logistic regression models. Specifically, we fit logistic regression models for the probability of censoring at each visit given mRS at the previous visit, study arm, and baseline variables, among those who attended the previous visit. Each model includes main terms and an intercept, e.g., the model

 $Pr(C_{365}=1 | C_{180}=1, B, A, M_{180}) = logit^{-1}(\beta_0 + \beta_1 B + \beta_2 A + \beta_3 M_{180})$

for the probability of remaining uncensored at 365 days given 180-day mRS, study arm, and baseline variables, is fit among those uncensored at 180 days (C_{180} =1).

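### SAP 11.1 fills a missing 180-day mRS from day-30 attendance, not the day-30 score, contradicting its own description, and can fill a surviving patient as mRS 6

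*SAP*

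**What the plan says.** SAP 11.1 fills the interim visits in order, day 30 and then day 180, before the TMLE models are fitted. For day 180 the rule reads "Next, for visit v=180 days, we fit a multinomial logistic regression for" M180, with A, B and C30 as the listed predictors, fitted among patients whose 180-day score was recorded. A patient without one receives "the value with highest predicted probability from the model fit". The models contain main terms for the listed variables only, and the 30-day score M30 is not listed.

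Earlier in 11.1 the C variables are defined as indicators: C180 = 1 "means the participant attended the 180-day visit and had his or her mRS" recorded. C30 is the day-30 equivalent. It is a yes/no variable and carries no score.

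Two other statements in 11.1 describe something different. The adjustment for dropout uses models "based on mRS measured at the previous visit, study arm, and baseline variables". The paragraph on intermittent missing data closes by calling the filled score "predicted by the above process based on previous mRS measurements, study arm, and baseline variables".

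The 365-day outcome is excluded from the fill. Model (1), for the 365-day outcome, takes the 180-day score as a categorical covariate. It gains one extra term, C30 times C180, and that term's interaction with arm, to mark filled scores.

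**The concern.** A programmer who follows the rule codes a different model from the one the SAP describes. The predictor left out is the patient's own earlier score, which is the variable the adjustment was built around.

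The second part concerns death. SAP 2.1 notes: "Although the mRS includes a category for death". Category 6 is therefore an available class in the multinomial model if patients who have died are entered as mRS 6 at day 180. Nothing in 11.1 removes that class for a patient known to have survived the visit. The rule is written for gaps that include a missed day 180 followed by an assessed day 365, and for that patient a 180-day score of 6 is impossible.

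At stake is the correctness of a prespecified step in the primary analysis and, to a lesser degree, the fit of model (1).

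**Working it through.** **Same fill for different patients.** For category k the linear predictor of the rule as written is a_k + b_k·B + c_k·A + d_k·C30. Take two patients with equal A and B who both attended day 30, one with M30 = 1 and one with M30 = 5. Both have C30 = 1, so all seven category probabilities are equal and so is the most probable category. No data are needed to show this.

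**How often the fill is mRS 6.** The SAP states no figure to reproduce, so this was simulated.
- From the documents: N = 500 (SAP 5.2), the multinomial model and the most-probable-category rule (SAP 11.1).
- Assumed: the mRS distribution, covariate effects, visit-to-visit correlation, 3% of patients (15 per trial) alive with day 180 missing, deaths recorded as mRS 6, and death by day 180 of 10% to 30%. The documents' text gives MISTIE II mortality at 30 days (10% medical, 15% surgical; Protocol 2.2) but no 180-day figure.
- Each setting had 25 trials, giving 25 × 15 = 375 living patients with a missing 180-day score.

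| Assumed death by day 180 | Filled as 6, with C30 | Filled as 6, with M30 in place of C30 |
|---|---|---|
| 10% | 8/375 = 2.1% | 1/375 = 0.3% |
| 15% | 30/375 = 8.0% | 5/375 = 1.3% |
| 20% | 59/375 = 15.7% | 21/375 = 5.6% |
| 25% | 81/375 = 21.6% | 31/375 = 8.3% |
| 30% | 119/375 = 31.7% | 67/375 = 17.9% |

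The fill fell on the correct side of the 0-3 versus 4-6 split in 61% to 72% of cases with C30 and 74% to 78% with M30. Using M30 reduces the impossible fills but does not remove them; that needs a rule based on vital status.

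**Effect on the estimate.** Two further simulations, also on assumed inputs, carried the fill through to the risk difference.
- One ran the SAP 11.1 estimator with N = 500, 120 trials per setting, 15%, 20% or 25% dead by day 180, and about 8 to 47 living patients per trial missing day 180. The C30 rule filled 14% to 35% of them as 6. Compared with using the true 180-day score, the risk difference moved by 0.01 to 0.10 percentage points on average, at most 0.6 in one trial, against an SD of about 4 points. The M30 rule moved it by almost the same amount.
- The other filled about 21% to 23% as 6 with C30 and under 1% with M30. The average shift was below 0.02 points and the largest 0.43, again with an SD of about 4.

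Confidence interval coverage was not checked in the run of the SAP estimator, and none is reported for the other.

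**Scale in patients.** SAP 9.0 cites 2% loss to follow-up in CLEAR III: 0.02 × 500 = 10 patients. At 2% to 35% filled as 6, that is 0.2 to 3.5 patients. The 2% is a guide and not a bound, because Protocol 4.3.2 counts a subject as lost only when there is no contact at day 365. A missed day 180 is not counted.

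**The case against.** The strongest reply is that this is a slip of notation with no visible consequence. C30 may simply stand where M30 was meant: the closing sentence and the stated purpose of the adjustment both point to M30. The filled score is a covariate, the outcome is never filled, model (1) marks filled scores, and the simulated shift is tiny. The size argument stands. The slip argument explains the conflict but does not remove it, since the text to be coded still names C30. The marker is only a partial remedy: it does not interact with the 180-day category, so a living patient filled as 6 shares the category-6 coefficient with patients who have died, none of whom can reach mRS 0-3 at day 365.

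Three stronger readings are tempting, and the documents do not support them.
- *Everyone with a missing 180-day score was alive.* Protocol section 8 lets a subject withdraw to the point of no contact at all, so vital status can be unknown. The fill is certainly impossible only for patients known to be alive after the visit.
- *The bootstrap leaves out the uncertainty of the fill.* SAP 11.1 places the missing-data steps ahead of the others, which could put them outside the resampling. It also presents them as part of the primary analysis, and each resample recomputes the estimator. Either reading is possible, so this is an ambiguity.
- *A fixed share, such as one in five, is filled as dead.* That share depends on the assumed mortality and covariate effects.

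**Conclusion.** The point holds as an error in the written rule. The day-180 fill conditions on attendance where the SAP says it conditions on the earlier score, and it allows mRS 6 for a patient known to have survived. The first part follows from the text alone. The second also assumes that deaths enter the fit as mRS 6 at day 180; the SAP does not say how C and M are set at visits after a death.

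The expected effect on the primary risk difference is small, about 0.1 percentage point or less on average in simulations whose inputs are mostly assumed. It would matter more if many patients missed day 180. This is a minor defect in a primary-analysis rule, worth correcting because the correction is nearly free. It is not evidence that the primary result would be materially biased.

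**What to change.** In SAP 11.1:
1. Fit the day-180 model on A, B, M30 (observed or filled) and the C30 indicator.
2. At each interim visit, exclude category 6 for any patient known to be alive after that visit, for example from the day-270 telephone contact or the day-365 visit. Take the most probable of the remaining categories.
3. State how C and M are set at visits after a death.
4. State that the fill is repeated within each bootstrap resample.

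The cost is a few sentences of SAP text and minor code, with no new data collection. The change should be made before treatment codes are opened, so that it cannot appear to be driven by results. Reporting the number of filled interim scores by arm would let readers judge how little depends on the rule.
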